All interventions will involve 4 weeks of group treatment consisting of two 1-hour group sessions per week and additional practice at home between sessions. The **Executive Training** condition will consist of the ET intervention that I previously developed and evaluated.^[7] ET sessions consist of 50% of the session practicing computerized cognitive training exercises, and 50% of the session developing cognitive strategies to use in the computerized exercises. Participants are encouraged to complete 40 minutes of computerized training per day, and complete strategy worksheets, at home between sessions. In **Computerized Cognitive Training only** participants will spend the entire one-hour session practicing computerized training exercises. Between sessions participants will be encouraged to practice the computerized exercises at home for 40 minutes per day. There will be no strategy development in this condition. In **Strategy Development only** participants will engage in cognitive strategy discussions to develop new executive function strategies that can be used in daily life. Between sessions, participants will be encouraged to practice their cognitive strategies in their daily life and track their strategies using the strategy worksheet. There will be no computerized cognitive training in this condition. All interventions will be delivered virtually in the participant's home and group sessions will be conducted using the online platform Zoom.

Outcome Measures

The primary outcome measure is community functioning measured using the Specific Levels of Functioning scale which will be rated by a participant's case manager who is familiar with their everyday activities and independent from the trial. I have successfully used this method of objectively measuring functioning in several previous studies.^[7,8]

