defeating attitudes theorized to underlie clinical depression and anxiety. The BCSS assesses four dimensions of self and other evaluation: negative-self, positive-self, negative-other, and positive-other. The GSES assesses optimistic self-beliefs to cope with a variety of difficult demands in life. The CFQ was designed to measure perception, memory, and motor lapses in daily life. The NCS measures "the tendency for an individual to engage in and enjoy thinking." The DAVOS measures cognitive biases and discriminates between schizophrenia spectrum patients and normal control subjects. The MAP-SR assesses the motivation and pleasure domains of negative symptoms.

Visits and Rationale

Visits: All interventions will involve 4 weeks of group treatment consisting of two 1-hour group sessions per week and additional practice at home between sessions.

Rationale: In order to further increase the efficiency and effectiveness of ET it is necessary to determine the active component of treatment. It is unclear whether both components are necessary to stimulate neurophysiological changes and improve functioning or whether one component drives the observed treatment effects. Dismantling ET will provide critical information regarding whether a single component is necessary or whether it is the interaction of these components that results in effective CR. Therefore, the proposed number and length of sessions are justifiable because the proposed number and length of sessions are congruent with ET and will allow the present research questions to be addressed.

Data Collection, Storage, Privacy, Destruction

Privacy: Information provided will not have any identifying features on it. A random code will be assigned to each participant and those numbers will be used to refer to a participant's data. The document linking names to codes will be kept in [name] locked laboratory on a password protected computer.

Limits to Confidentiality: Limitations that will require confidentiality to be broken include: if a research member is aware of child abuse where the child might still be a risk, if a participant expresses that they are risk of harming themselves or others, and if a participant expresses that another health professional has engaged in sexual abuse.

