Data Storage: All de-identified forms will be kept in a locked cabinet where only members of the research team have access to it. Information kept on a computer will be password protected. All filing cabinets and computers will be located in [name] locked laboratory that only research staff have access to. All research staff receive data protection and confidentiality training and sign a confidentiality form.

Data Retention/Destruction: De-identified data will be kept for seven years before being destroyed. Only members of [name] lab will have access to the data.

STUDY ANALYSIS

Sample size Statistics

90 participants with schizophrenia-spectrum disorders will be recruited. Power analyses, conducted with GPower, indicate that 90 participants (30 per treatment condition), accounting for an upper limit of 25% attrition observed in my previous trials of ET,^[7,8] provides 80% power to detect a medium effect size (Cohen's $f = 0.2$) difference between conditions.

Statistical Plan

Primary and secondary outcomes will be examined using Linear Mixed Models on the Intent-to-Treat sample with missing data interpolated using maximum likelihood estimation. The primary endpoint is the 3-month follow-up assessment, and secondary endpoint of post-treatment will also be examined.

STUDY ETHICS

Potential Benefits

The direct benefit to the participant includes improvements in attention, memory and problem solving, caused by the treatment. Also, if the results are released to the participant's clinical treatment team, they can use it to help with the ongoing care. There is also a potential benefit to the scientific community because the results may help in understanding individual differences.

Potential Risks

Psychological/emotional risks may arise during assessment procedures due to frustration or embarrassment during the neurocognitive assessment trials. Participants may feel uncomfortable discussing personal topics related to their symptoms or they may become tired. These risks are equal to those that occur within the clinical context. Participants will be reminded that they are able to stop the interview at any time to take a break or to postpone the procedure to a different day. Participants will also be given the phone number of a mental health professional if discomfort does occur.

Safety Provisions

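### All three arms are treated in groups, but the Statistical Plan names no therapy-group term; a participant-level mixed model would satisfy it and could give standard errors that are too small

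*Combined protocol and SAP*

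**What the plan says.** Study Intervention/Standard of Care states that "All interventions will involve 4 weeks of group treatment consisting of two 1-hour group sessions per week", and Visits and Rationale repeats it: "Visits: All interventions will involve 4 weeks of group treatment". Under Randomization, individual participants are allocated to the three conditions.

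The session formats differ by arm:
- **Executive Training (ET):** "ET sessions consist of 50% of the session practicing computerized cognitive training exercises"; the other half is strategy work.
- **Computerized training only:** the whole hour is exercises. "There will be no strategy development in this condition".
- **Strategy development only:** "participants will engage in cognitive strategy discussions to develop new executive function strategies that can be used in daily life". "There will be no computerized cognitive training in this condition".

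On analysis, the Statistical Plan has two sentences. The first says "Primary and secondary outcomes will be examined using Linear Mixed Models on the Intent-to-Treat sample" and covers missing data by maximum likelihood. The second makes 3-month follow-up the primary endpoint and post-treatment the secondary one. Sample size Statistics gives GPower, N = 90 (30 per arm), 80% power, f = 0.2 and an allowance for 25% attrition. Neither section mentions therapy group, group size, ICC or a design effect, and no other section addresses clustering.

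**The concern.** Participants are randomized one by one and then treated together. Members of a therapy group share a facilitator, a session dynamic and each other, so their outcomes may be correlated. A session cannot at once be all exercises, all strategy discussion and half of each, so a group can in practice serve only one arm. Any between-group variance then falls entirely into the arm comparison.

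A mixed model with participant effects alone, which is a common reading for repeated measures, treats the 30 participants in an arm as independent. With positive within-group correlation its intervals for arm differences are too narrow and its tests reject too often. The trial exists to attribute benefit to one component or to the combination by comparing arms, so a chance difference between a few groups could be credited to a component. If group membership is not recorded, the analysis cannot be repaired later.

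**Working it through.** **1. The plan's own figure.** The GPower settings are not stated. A repeated-measures within-between interaction with 3 arms, 2 measurements, correlation 0.5 and alpha 0.05 (all assumed) comes close:
- noncentrality = f² × N × 2/(1 − r) = 0.04 × 66 × 2/0.5 = 10.56; with 2 and 63 df, power is 0.818;
- allowing for attrition, 66/0.75 = 88, against the stated 90.

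That calculation treats participants as independent. It does not prove that clustering was ignored, because other settings give other numbers (with 3 measurements, 54 completers and 54/0.75 = 72 recruited). What can be said is that no allowance for clustering is visible.

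**2. Design effect.** From the documents: 30 per arm, 25% loss, hence 90 × 0.75 = 67.5 expected completers. Assumed: closed groups of n = 5, 6 or 10, and the ICC values. With random loss the size-weighted mean group size is m = 0.25 + 0.75n = 4.0, 4.75 and 7.75. The design effect is DE = 1 + (m − 1) × ICC, and the effective number of completers is 67.5/DE.

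| ICC | Quantity | n = 5 | n = 6 | n = 10 |
|---|---|---|---|---|
| 0.01 | DE | 1.03 | 1.04 | 1.07 |
| 0.01 | Effective completers | 65.5 | 65.1 | 63.2 |
| 0.05 | DE | 1.15 | 1.19 | 1.34 |
| 0.05 | Effective completers | 58.7 | 56.8 | 50.5 |

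**3. Type I error with group ignored, single time point.** Simulated null trials, 3 × 30 participants, each lost with probability 0.25, one-way F test at alpha 0.05, 100,000 trials per scenario:

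| ICC | n = 5 | n = 6 | n = 10 |
|---|---|---|---|
| 0 | 5.1% | 5.1% | 5.0% |
| 0.01 | 5.5% | 5.6% | 6.0% |
| 0.05 | 7.4% | 8.0% | 10.6% |
| 0 computerized / 0.025 ET / 0.05 strategy | 6.3% | 6.5% | 7.7% |

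Groups of 3 at ICC 0.05 give about 6%.

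**4. Longitudinal model.** Baseline, post-treatment and 3 months; 12.5% lost before post-treatment and 25% by 3 months; group effect on the two follow-up visits only; unstructured participant covariance, REML, Kenward-Roger; 6,016 null trials per scenario (Monte Carlo standard error about 0.3 points).
- At ICC 0.05 and visit correlation 0.5, the 3-month test across arms rejects in 7.7%, 8.6% and 11.4% of trials (n = 5, 6, 10).
- Model-based over true standard error is then 0.926, 0.900 and 0.847, so standard errors are about 7%, 10% and 15% too small.
- The result depends on the visit correlation. At 0.3 and 0.7 the rejection rate is 7.1% and 10.0% (n = 5), or 9.7% and 15.6% (n = 10).
- At ICC 0 the three group sizes give 5.7%, 4.9% and 5.2%, although group size cannot matter there. This run therefore cannot resolve ICC 0.01 from ICC 0, and step 3 should be used for low ICCs.

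**The case against.** **The plan is silent rather than wrong.** A reader might infer that the plan prescribes an incorrect analysis. It does not: a linear mixed model can hold a group effect, and its covariance structure and baseline handling are equally unstated. That stands, and the point is confined to a term the plan does not require. It is still more than brevity, because the plan followed as written permits intervals that are too narrow.

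**Nesting is inferred.** The documents never say that groups are formed by arm. Nor is the content exclusive to an arm, since ET contains both other arms' components. It is the session format that cannot be shared. With that wording the inference is strong.

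**The ICC may be low.** The primary outcome is rated by a case manager independent of the trial. Computerized-only sessions are exercises, as is half of each ET session. In both of those arms home practice is encouraged at 40 minutes per day: "Between sessions participants will be encouraged to practice the computerized exercises at home for 40 minutes per day" in the computerized-only arm, and similarly in ET. If followed for 28 days this is 40 × 28/60 = 18.7 hours, against 2 × 4 = 8 hours in group. All of this stands and favours the lower rows of the ICC range. Against it, strategy-only sessions are group discussions, and many secondary outcomes are self-reported, so the independent rater does not protect them. The documents cannot show that the ICC is negligible, or that it is large.

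**Power.** A reader might infer that N = 90 is inadequate. The documents do not support that: the ICC is unknown, and any power percentage would depend on unstated GPower settings.

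**Conclusion.** The point holds as a cheap improvement. The plan does not require a therapy-group term in a design where group is, by inference, nested within arm, and its sample-size statement shows no allowance for clustering. There is no inflation at ICC 0. It is small at ICC 0.01, and small for groups of 3 even at ICC 0.05. It becomes material with larger groups and an ICC near 0.05. If the ICC varies by arm as the session formats suggest, the single-time-point error is about 6-6.5% (groups of 5-6) or 8% (groups of 10). Every one of these figures rests on assumed group sizes, ICCs, closed groups, random loss and alpha 0.05; the longitudinal ones also rest on an assumed visit correlation. Confidence that the term is missing is high; confidence in the size of the effect is limited.

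**What to change.** - Record a therapy-group ID for each participant. State the planned group size and whether groups are closed or rolling; if rolling, define the cluster in advance.
- Prespecify a random effect for therapy group within arm on the post-treatment and 3-month outcomes, with Kenward-Roger or Satterthwaite degrees of freedom. Say whether its variance is common to the arms.
- Fix one rule for a group variance estimated at zero: report the participant-level test in that case. The rule will be needed, since the estimate was at or below zero in 9-56% of simulated trials, depending on scenario.
- Report the ICC, with an analysis of group means as a sensitivity check.
- Keep N = 90. State the GPower settings, say that the power figure makes no visible allowance for clustering, and restate power over an assumed ICC range such as 0.01-0.10. If it falls below 80%, report that as a limitation.

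Across 19 longitudinal scenarios, including those with ICC differing by arm, the random effect with this rule had type I error of 3.3-5.6%, and the group-means test 4.3-5.7%.

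**Cost.** One data field, one model term with its rule, and a revised power statement. Intervals widen somewhat. Median denominator degrees of freedom fall from about 73 to 28-38 (groups of 5-6) or 15-21 (groups of 10) for ICC 0-0.05. If the true ICC is 0, the test is slightly conservative (3.3-4.7% in place of 5%).

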Cognitive remediation (CR) is a psychological intervention based on principles of learning and neuroplasticity to improve neurocognitive abilities with the ultimate goal of improving community functioning. The neuroplastic effects of CR are well established with evidence for increased gray matter volume in the hippocampus and amygdala,^[5] increased activation of the medial prefrontal cortex,^[6] and increased amplitude of the mismatch negativity event-related potential^[7] following CR. In two recent randomized controlled trials (RCTs), I also demonstrated that CR improves synchronization of neural networks in the alpha and theta frequency bands.^[7,8] Meta-analyses support moderate transfer of these neurophysiological improvements to neurocognitive abilities ($d = 0.45$) and community functioning ($d = 0.37$).^[9] In a recent systematic review, I reported that CR approaches vary widely, but approaches that incorporate training of executive functions are generally the most effective.^[10] Based on these findings **I developed a novel CR intervention specifically targeting executive functions** and conducted two double-blind RCTs, in which targeted executive function training (ET) produced greater improvements in neurophysiology, neurocognition, functional skills and real-world community functioning compared to other leading forms of CR.^[7,8] This intervention is approximately half the duration of other CR programs, yet produces larger effect size improvements in community functioning.

Justification for Research

In order to further increase the efficiency and effectiveness of ET it is necessary to determine the active component of treatment. There are two primary components of ET and neither have ever been examined in isolation: 1) computerized cognitive training, and 2) strategy development. It is unclear whether both components are necessary to stimulate neurophysiological changes and improve functioning or whether one component drives the observed treatment effects. Dismantling ET will provide critical information regarding whether a single component is necessary or whether it is the interaction of these components that results in effective CR.

This will be the first study to dismantle CR and examine components necessary to effectively improve neurocognition and functioning for individuals with schizophrenia. These findings will directly inform methods of improving CR efficacy.

Purpose and Hypotheses

The primary goal of this study is to:

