- (1) Examine the efficacy of computerized training alone, compared to strategy monitoring alone, compared to full ET on neurocognition, and functioning.

STUDY DESIGN

Sample Size/Subject Selection

90 participants with schizophrenia-spectrum disorders will be recruited.

Inclusion Criteria

The target population for this study are those who meet the criteria for schizophrenia based on the DSM-V diagnosis. The inclusion criteria is anyone who meets the criteria of schizophrenia, schizoaffective disorder or any other psychotic disorder, are also 18-65 years of age, know how to use a computer, are not abusing drugs or alcohol and can read and speak English.

Exclusion Criteria

Exclusion criteria include anyone enrolled in a cognitive training program in the last 6 months, anyone with a neurological disease or neurological damage, medical illnesses that can change neurocognitive function, medical history of head injury with loss of consciousness and those with physical handicaps.

Method of Recruitment

The participants will be recruited from various sources including mental health agencies and referrals from mental health providers.

Limitation of the study

The primary limitation of the study will be attrition if participants do not complete the study or the follow-up assessment.

Informed Consent

A consent form will be given to all participants to sign. The language of the consent form will be written at an elementary school level. A research assistant will read out the consent form to participants and will clarify anything and answer any participant questions. They will also ask the participant questions during the consenting process to ensure that the participant understands. Participants will also be reminded that it is their right to refuse to participate or withdraw from the study and that doing so will not affect their existing treatments or services.

STUDY PROCEDURE

Randomization

Participants will be randomized to receive Computerized Cognitive Training only, Strategy Development only, or both (ET).

Study Intervention/Standard of Care

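### Must the plan name its arm contrasts, a multiplicity rule and a criterion for calling one component enough?

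*Combined protocol and SAP*

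**What the plan says.** The aim is stated under Justification for Research and again under Visits and Rationale: it is open "whether both components are necessary to stimulate neurophysiological changes and improve functioning or whether one component drives the observed treatment effects". Purpose and Hypotheses turns this into one goal: "Examine the efficacy of computerized training alone, compared to strategy monitoring alone, compared to full ET on neurocognition, and functioning". Randomization gives three arms (computerized training, strategy development, and the two together as ET); no arm receives neither component.

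Outcome Measures fixes one primary outcome, the Specific Levels of Functioning scale (SLOF), rated by a case manager independent of the trial. The Statistical Plan is two sentences long. The first says that "Primary and secondary outcomes will be examined using Linear Mixed Models on the Intent-to-Treat sample", with maximum likelihood for missing data. The second says that "The primary endpoint is the 3-month follow-up assessment, and secondary endpoint of post-treatment will also be examined". Sample size Statistics says that 90 participants, 30 per arm and allowing for up to 25% attrition, "provides 80% power to detect a medium effect size" (Cohen's f = 0.2) between conditions.

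The document gives no alpha, named primary contrast, rule for the arm pairs, margin, or table linking results to conclusions.

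**The concern.** A dismantling trial can end with one of two headline claims: both components are needed, or one is enough. The second is a claim of no meaningful difference, and a difference test alone cannot support it. Because no arm goes without both components, similar results could also mean that the arms are equally ineffective.

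The awkward result is ET significantly ahead of exactly one component. That pattern is common when ET truly leads both arms and also when one component truly equals ET. With no rule set beforehand, an author could read the non-significant contrast as proof that the other component suffices. Separately, testing three pairs at 5% each with no protection would push the chance of a false positive above 5%.

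**Working it through.** **1. What test the sample size implies.** Stated inputs: three arms, f = 0.2, 80% power, 25% attrition, 90 recruited. Assumed inputs: alpha 5%, two measurements, visit correlation rho = 0.5. For an arm-by-visit interaction the noncentrality is f² × N × m / (1 − rho).

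- N = 66: 0.04 × 66 × 2 / 0.5 = 10.56. With 2 and 63 df, power is 0.818.
- Recruitment: 66 / 0.75 = 88, close to the planned 90.
- A one-way comparison at a single visit would need 244 completers, so it does not explain 90.

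The plan's figure therefore fits an overall 2-df test. This is an inference, because the document does not state the test.

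**2. What f = 0.2 means for one pair.** If one arm stands apart from two equal arms by d, the SD of the three means is d × √2/3 = 0.471d. In this power convention with two visits, f is half of that, 0.2357d, so d = 0.2 / 0.2357 = 0.85 SD.

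**3. Multiplicity.** Simulated family-wise error with all arms equal:

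| Procedure | Error |
|---|---|
| Three pairs, no gate | 12% |
| Two ET pairs, no gate | 9% |
| Pairs only after a significant overall test | 5% |

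The gate is enough with three arms. If all are equal, the overall test holds 5%. If only two are equal, a single true null remains and it is tested at 5%.

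**4. Pairwise precision.** With 67 completers (arms of 23, 22 and 22), the half-width is 1.998 × SD × √(1/23 + 1/22) = 0.596 × SD.

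- Change score, rho 0.5: SD = √(2 × 0.5) = 1, giving 0.60.
- Baseline-adjusted, rho 0.5: SD = √(1 − 0.25) = 0.866, giving 0.52.
- Baseline-adjusted, rho 0.7: SD = √(1 − 0.49) = 0.714, giving 0.43.

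**5. How often each pattern occurs.** Simulation with the same arms and two-sided 5%. The true leads are assumptions. The 0.37 is borrowed from the Background, where it is the meta-analytic effect of cognitive remediation on functioning, not a contrast between components. The share is the proportion of trials with a significant overall test in which ET beats exactly one arm.

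| ET's true lead over both arms | Result | Change score, rho 0.5 | Adjusted, rho 0.5 | Adjusted, rho 0.7 |
|---|---|---|---|---|
| 0.37 SD | beats both | 11% | 15% | 24% |
| | share | 53% | 49% | 42% |
| 0.50 SD | beats both | 22% | 31% | 48% |
| | share | 44% | 37% | 28% |
| 0.85 SD | beats both | 69% | 82% | 95% |
| | share | 17% | 11% | 4% |

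If one component truly equals ET and the other is 0.74 SD worse, ET beats exactly one arm (with the overall test significant) in 59%, 73% and 88% of all trials. The pattern is therefore ambiguous.

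**6. Would a sufficiency margin help?** For a margin of 0.37 SD (illustrative), true difference zero, one-sided 2.5%, 80% power and SD 1, n per arm = 2 × (1.96 + 0.842)² / 0.37² = 115. With 25% attrition the total is 3 × 115 / 0.75 = 460. At 22 to 30 per arm, power is 23% to 30%. Baseline adjustment at rho 0.7 raises it only to 41% to 52%.

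**The case for a change.** The strongest case for a change is that the omission depends on none of these assumed figures, that a few sentences would mend it without new data, and that a decision rule is credible only if written before the data are seen. At modest true leads the ambiguous pattern makes up around half of the positive trials. All of that is accurate, and a fuller SAP would be better practice.

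Three things weaken it.

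- The harm needs a step that the plan does not take. No section says that a non-significant ET contrast will be read as showing that one component suffices, or that pairs will be tested without a gate.
- The suggested rule would not change how often the ambiguous pattern appears. The model, the three differences and their intervals stay the same; only the label changes.
- A rule that declares both components needed whenever ET beats each arm would itself overreach. With no arm lacking both components, that result shows ET superior to each component as delivered. Study Intervention/Standard of Care also gives ET both kinds of home practice and each single arm only its own, so total workload may differ.

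What stands is a caution for the reader: a non-significant ET contrast in this trial is inconclusive.

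**Conclusion.** No change is called for. The plan leaves out detail; it does not state a wrong rule. It names the arms to be compared and fixes one primary outcome and one primary time point, so the only multiplicity in the primary analysis is across the three pairs. The analysis that fits its sample size, an overall test followed by pairs, keeps family-wise error at 5%. A competent analyst would fill the rest in the usual way, reporting all three differences with intervals and treating non-significance as non-significance.

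The real limit is size. Under an assumed alpha of 5%, 67 completers and rho of 0.5 to 0.7, with either a change score or baseline adjustment, pairwise intervals run from ±0.43 to ±0.60 SD. ET beats both arms in 11% to 24% of trials at a true lead of 0.37 SD, and in 69% to 95% at the 0.85 SD that f = 0.2 appears to imply. A formal sufficiency claim at a 0.37 SD margin would need about 115 completers per arm against about 22 expected, so writing one in would gain little. The view would differ if the plan had said that a non-significant contrast would count as proof that one component is enough.

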All therapists and lab staff will be trained in suicide risk assessment procedures. Therapists will follow established protocols to conduct a risk assessment if there is any indication of suicide risk. Therapists will create a safety plan with the participant if risk is low or moderate. If risk is high, then therapists will collaboratively discuss the risk with the participant and escort participants to the emergency department at the respective hospital site (CAMH, Ontario Shores, or Scarborough Health Network). If a risk assessment is required during an assessment, one of the assessors will conduct an initial assessment with the participant. If risk is above minimal, assessor will immediately consult with [name] on the best course of action before continuing the assessment. If risk is determined to be high then the participant will be collaboratively escorted to the emergency department.

During the consenting process participants will be asked comprehension questions about the consent form to ensure participants are aware of what they are consenting to.

Ethics Approval

This protocol is currently under review at the University of Toronto Research Ethics Board. Approval from the University of Toronto REB will be forwarded to Ontario Shores Centre for Mental Health Sciences upon approval.

Dissemination

Results from this research will be presented at academic conferences and submitted for publication at peer-reviewed journals.

Statement of Right to withdraw from the study

Participants can withdraw from the study at any time. If participants decide that they would like to withdraw their data from the study, then their data will be destroyed.

REFERENCES

- [1] Wu, E. Q. et al. The Economic Burden of Schizophrenia in the United States in 2002. *J. Clin. Psychiatry* 66, 1122–1129 (2005).
- [2] Palmer, B. A., Pankratz, V. S. & Bostwick, J. M. The Lifetime Risk of Suicide in Schizophrenia: A Reexamination. *Arch Gen Psychiatry* 62, 247–253 (2005).
- [3] Eack, S. M. & Newhill, C. E. Psychiatric Symptoms and Quality of Life in Schizophrenia: A Meta-Analysis. *Schizophr. Bull.* 33, 1225–1237 (2007).
- [4] Swartz, M. et al. Effects of Antipsychotic Medications on Psychosocial Functioning in Patients with Chronic Schizophrenia: Findings from the NIMH CATIE Study. *Am J Psychiatry* 164, 428–436 (2007).

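### The therapist's step at high suicide risk, escorting the participant to the emergency department, does not fit treatment delivered by Zoom to the participant's home

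*Combined protocol and SAP*

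**What the plan says.** Two sections of the combined protocol and SAP bear directly on the point.

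- **Delivery (Study Intervention/Standard of Care).** Treatment is "4 weeks of group treatment consisting of two 1-hour group sessions per week", with practice at home in between. On the mode of delivery the section states "All interventions will be delivered virtually", places the participant at home, and adds that "group sessions will be conducted using the online platform Zoom". No arm, site or session is excepted.
- **High suicide risk (Study Ethics, Safety Provisions).** For therapists the section begins: "Therapists will follow established protocols to conduct a risk assessment if there is any indication of suicide risk". At low or moderate risk the therapist makes a safety plan with the participant. At the top level the instruction is: "If risk is high, then therapists will collaboratively discuss the risk with the participant and escort participants to the emergency department". The destination is the participant's respective hospital site, one of three that are named.

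The same section has a separate rule for risk found at an assessment visit: "If a risk assessment is required during an assessment, one of the assessors will conduct an initial assessment with the participant". That rule also ends in an escort when risk is high.

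**The concern.** The protocol assigns its most serious safety response to a person who, on the plain reading of the delivery section, is on a video call and not in the room. A therapist who judges risk to be high during a Zoom session is given an instruction that does not match the setting and no account of how to carry it out there. The therapist would have to improvise at the point where the protocol most needs to be unambiguous.

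The protocol itself treats suicide risk as foreseeable: it trains all therapists and laboratory staff in risk assessment and grades the response by level. The affected step is therefore part of its planned safety process. Randomisation, the endpoint, power and the analysis are not affected.

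**Working it through.** The plan states no figure to reproduce on this point. The check is a comparison of text, plus one count of how much treatment contact is involved.

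**1. Which contact does the therapist rule govern?** Safety Provisions has one rule for therapists and another for risk that arises during an assessment, where an assessor acts first. The natural reading is that the therapist rule governs treatment sessions.

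**2. How is that contact delivered?** Virtually, to the home, on Zoom, in all three arms. The document does not say outright that therapist and participant are in different places, but virtual delivery by Zoom to the home has no other natural meaning.

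**3. What does the step require?** To escort someone to a hospital is to accompany them in person. A therapist on a video call cannot do this as written. The other parts of the therapist procedure (risk assessment, safety plan, discussion of the risk) do not by their wording need the two people to be in one place, so the mismatch is confined to the escort.

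**4. Does any other text supply a remote version?**

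| Text | What it covers | Why it does not fill the gap |
|---|---|---|
| Established protocols (Safety Provisions) | Conducting the risk assessment | Content not reproduced; the step after a high-risk result is written out separately, and it is the escort |
| Limits to Confidentiality: "Limitations that will require confidentiality to be broken include" the case "if a participant expresses that they are risk of harming themselves or others" | Disclosure when risk is expressed | Names no recipient and no next step |
| Telephone number of a mental health professional (Potential Risks) | Discomfort | Not tied to suicide risk or to the high-risk level |
| Case manager (Outcome Measures) | Rating the primary outcome | Not linked to a high-risk event |
| Clinical treatment team (Potential Benefits) | Possible use of released results in ongoing care | Not linked to a high-risk event |

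None of them does.

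**5. How much treatment contact is involved?** From the schedule in Study Intervention/Standard of Care, repeated under Visits and Rationale:

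- Sessions per participant = 4 weeks x 2 per week = 8
- Hours per participant = 8 x 1 hour = 8
- Sessions stated to be on Zoom: 8 of 8, on the same schedule in all three arms
- Treatment sessions stated to be in person: 0

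This is exposure only. With no rate of high-risk events in the documents, an expected number of affected participants cannot be calculated.

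**The case against.** The strongest reply is that this is an unexplained mechanism and not a contradiction. The direction at high risk is clear: discuss it, then get the participant to the emergency department at the respective site. Only the means is missing. The document never says that therapist and participant are apart, never limits the therapist sentence to Zoom sessions, and names local hospitals, so some local arrangement may be intended. The established protocols and the staff training could cover remote escalation, and a short protocol may properly leave such detail to operating procedures. Some pages, including the consent pages, were not available to this review. With no event rate, and nothing affecting the trial's inference, a request for clarification might seem enough. The count of 8 sessions, it can be added, only restates that all delivery is virtual.

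Part of this stands. Separate locations and the scope of the therapist sentence are inferences, though natural ones. Absence can be claimed only for the text available. The count shows reach, not risk.

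The rest does not answer the point. The protocol is not silent on the high-risk step: it states one, and the one it states presupposes physical presence. The established protocols are invoked for conducting the assessment, not for what follows it. If a remote procedure does exist elsewhere, the protocol's own instruction would still be the escort and would still need to be brought into line. A safety instruction should not depend on the reader supplying its meaning during an event.

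**Conclusion.** The point holds: the high-risk step for therapists is wrong as written for the delivery mode the protocol specifies. It reaches all 8 scheduled group sessions per participant in all three arms. The number of participants who would meet it is unknown.

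The conclusion rests on three readings: that escorting means accompanying in person, that the therapist rule applies to treatment sessions, and that therapists join the Zoom sessions from somewhere other than the participant's home. It is limited in two ways. The absence of a remote procedure is asserted only for the text available. No mismatch is claimed for the assessor's escort rule, because the document does not say whether assessments are in person or remote.

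It should be corrected despite the unknown frequency, because it concerns the highest level of suicide risk the protocol defines.

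**What to change.** Reconcile Safety Provisions with Study Intervention/Standard of Care, so that the step stated for high risk in a treatment session is one that can be carried out under the stated mode of delivery. If a separate operating procedure already deals with this, the protocol should refer to it at the high-risk step and its own wording should agree with it. The content of the procedure is a clinical and ethical matter for the investigator and the ethics board, and none is proposed here.

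The Ethics Approval section describes the protocol as still under board review. At that stage the change is one of wording; after approval it is an amendment. Any operational cost depends on the rule adopted and cannot be judged from the documents. The sample size and the statistical plan do not change.
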